114 We hypothesize that combat experiences, including stress and noise, alter functional connectivity within the A1/VAN. This 115 dysregulation contributes to tinnitus or PTSD, or both, resulting in common symptoms and clinical presentations. A1/VAN modulates hypo- and/or hyperactivity within other brain networks, resulting in symptoms of tinnitus and/or PTSD. We 116 hypothesize that the A1/VAN is a privileged network with a central role in the hypo- or hyper-activation of other networks, 117 directly or indirectly; thus, it influences tinnitus sensation, tinnitus-related distress, and PTSD. Dysregulation of specific 118 119 brain regions within A1/VAN is the neurobiological mechanism responsible for comorbid tinnitus and PTSD, and suggests 120 a different phenotype among such individuals, which may help explain high rates of non-response to PTSD treatment 121 (Steenkamp & Litz, 2020). We will examine the overlapping and unique symptoms between both disorders, the neurobiological similarity between tinnitus and PTSD, and model psychometric and neurofunctional data. 122

123 124 **5**. RESEARCH DESIGN

We propose a phenotyping and neuroimaging study, examining shared and unique symptoms and neurobiological contributions for tinnitus and PTSD. We will recruit individuals with both tinnitus and PTSD (**T&P**), PTSD Only (**PO**), Tinnitus Only (**TO**), and Healthy Controls (**HC**) (30/group). After consent is provided, participants will be scheduled for audiometric evaluations and PTSD assessment to determine eligibility. Eligible participants will be assigned to one of the four groups and scheduled for an additional tinnitus psychoacoustic evaluation, when available, to demonstrate reproducibility. Resting-state fMRI (rs-fMRI) scans will be completed at this time. Study-related procedures will be completed within 4 weeks to decrease likelihood of drop-out.

132 133

113

Figure 1. Study Design Overview.

134 135

Group Assignment Neuroimaging Assessment & Eligibility Determination **Tinnitus and PTSD** Tinnitus Psychoacoustic (T&P; N = 30)**Evaluation;** Screening; No Tinnitus, PTSD Only **Resting-State Functional Comprehensive Audiometric** Magnetic Resonance (PO; N = 30)**Evaluation;** No PTSD, Tinnitus Only Imaging (fMRI) & PTSD Assessment (TO; N = 30)**Health Controls** (HC; N = 30)

136 137

138 6. RESEARCH PLAN

139140 6.1 Selection of Subjects

141

142 **6.1.1. Subject Population.**

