This study will consent and screen 160 veterans and active duty service members to include 120 for analysis. Subjects will be recruited from the San Antonio community. Women and minorities will be actively recruited into the study.

145

146 **6.1.2. Source of Research Material**.

147 All measures are being administered for research purposes. For a complete list of measures, see Section 6.2.

148

157

173

174

175

149 6.1.3. Inclusion and Exclusion Criteria.

150 **Inclusion Criteria**

- 151 • Male and female DEERS eligible veterans and active duty service members, ages 18 and above
- preferred language is English and able to read and speak English at a 6th grade level 152 •
- those with PTSD (T&P; PO) must meet full criteria for PTSD diagnosis based on the DSM-5 and assessed by an 153 • independent evaluator using the CAPS-5 154
- those with chronic, constant tinnitus (T&P, TO) will be identified by self-report and confirmed with the audiometric 155 • 156 assessment.

158 **Exclusion Criteria**

- psychiatric hospitalization in the last 12 months 159
- significant cognitive impairment determined by inability to comprehend screening assessment 160 •
- psychiatric problems and/or high suicide risk warranting immediate intervention 161 •
- 162 • neurobiological disorders, Meniere's disease
- 163 • Temporomandibular disorders that affect tinnitus, per self-report
- history of major head trauma with loss of consciousness for 20 minutes or more as determined by the History of Head 164 • Injuries questionnaire 165
- history of seizures 166 •
- 167 conditions that would prevent completion of fMRI scan (any type of electronic, mechanical, or magnetic implant, coil, • filter, or stent, any type of surgical clip or staple, shunt, any type of metal object, hearing aid, spinal fusion, halo vest, 168 169 IV access port, eyelid spring, artificial eye, artificial heart valve, biostimulator, severe hyperacusis)
- active conductive pathology/hearing loss as determined by audiometric assessment. 170 •
- Those with tinnitus (T&P; TO) will be excluded if their tinnitus is 171 • 172
 - 0 intermittent
 - objective or pulsatile 0
 - present for less than 6 months. 0

6.1.4. Description of the Recruitment and Prescreening Process. 176

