The study will be conducted in collaboration with the STRONG STAR Multidisciplinary PTSD Research Consortium. 177 Primarily potential participants will self-refer to the study. General announcements and flyers will be posted on public 178 media and at various community sites that will allow self-referral. One additional flyer will be posted to target potential 179 participants who do not meet criteria for PTSD and/or tinnitus. Potential participants may also self-refer in response to 180 181 recruitment information on the STRONG STAR website and social media. Potential participants may contact STRONG 182 STAR if they feel that they are eligible. In addition to self-referral recruitment study staff will work closely with staff at 183 hospital clinics (Mental Health Clinics, Substance Abuse Treatment Clinics, Primary Care Clinics, Audiology Clinics) and 184 Veteran advocacy groups, which have been found to be reliable and productive sources of participants. Approved flyers 185 will be posted within Brooke Army Medical Center and affiliated clinics, including primary care, preventive care, auditory, dental, pharmacy, CPT Jennifer Moreno Primary Care Clinic, and Westover Medical Home, after appropriate clinic 186 187 approval is obtained. Referring providers and staff can give their patients contact information for the study staff so that interested individuals may contact STRONG STAR directly. Providers can also obtain a "consent to contact" form 188 (Appendix A) from interested individuals so that study staff can contact them directly about study participation. In addition, 189 there may be community events where information about STRONG STAR studies is provided and those interested may fill 190 191 out the "consent to contact" form indicating that they would like a member of the research team to contact them at a later 192 date to learn more about the study and schedule or complete pre-screening (Appendix B).

193

Under an IRB approved HIPAA Waiver of Authorization, study personnel will conduct a brief telephone pre-screening or in-194 195 person screening where the basic study inclusion and exclusion criteria will be reviewed to help the individual determine if he 196 or she meets the study criteria or has obvious exclusions from the study protocol so as to prevent individuals from making

197 unnecessary travel for consent and more in-depth screening (see Appendix B). This information will be entered into a secure

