Potential participants will have the study explained to them in a safe and private location in person using a paper form at 215 the STRONG STAR offices or at the Hearing Center of Excellence or online using an electronic consent (eConsent). The 216 217 preferred method is to use the eConsent process. Potential participants will be provided a link to the informed consent 218 document (ICD) or will be given a hard copy of the informed consent document (ICD) to read. The research team member obtaining informed consent will then engage the potential participant in an interactive explanation of the study 219 guided by the ICD. After the subject has read the ICD, he or she will be given the opportunity to consider participation 220 221 and discuss the research with family and friends. The Research Team will be available to answer any questions about 222 the research. Once the potential participant has reached a decision, a member of the study team will review the risks and 223 benefits of study participation and ensure the participant has an understanding of the material discussed, and the risks and benefits of their potential involvement in the study. The participant will sign the consent form either electronically or 224 on a paper form. A copy of the signed ICD will be given to the participant. 225 226

227 6.1.6. Subject Screening Procedures.

Following consent, screening and assessment will take place to determine participant eligibility. The entire screening process will take approximately 5 hours. This will include the completion of the questionnaires and interviews outlined in the table in Section 6.2 below. This may occur in-person using paper forms or the participant will be logged into the STRONG STAR eCAP online data capture system to complete self-report questionnaires. For individuals not meeting study inclusion criteria, the Study Staff will assist coordinating appropriate care outside of the study.

233

If the participant has been referred from another STRONG STAR study and already completed assessments within the
 past 30 days, the participant will be asked as part of the consent process to use these assessments rather than repeating
 the assessment battery. If the participant is newly referred to this study, if it has been more than 30 days since
 completing the assessments for another study, or the participant declines use of previously completed assessments, he or

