 she will meet with an evaluator and complete the full baseline assessment per protocol.

239

240 **6.1.7. Compensation for participation**.

In accordance with the Defense Health Agency (DHA) Administrative Instruction (AI) Number 3200.01 dated 28 April 241 2022, all study participants will be compensated \$50 for the neuroimaging scan. As outlined in the DHA AI, for active duty 242 243 participants to receive compensation, they must not otherwise be scheduled to perform work during the neuroimaging 244 scan appointment. Payment will be provided via a rechargeable MasterCard® ClinCard. The MasterCard® ClinCard is a debit card issued to the study participant. Funds are loaded onto card through the ClinCard website at www.clincard.com. 245 246 Only authorized users will be able to access the ClinCard website to add funds with a username and password. The ClinCard funds will be available to recipients within 1 business day and can be used as the participant chooses. The 247 participant will be notified that their name, address and date of birth will be shared with a third-party (ClinCard) solely for 248 249 the purposes of payment processing. This information will only be used for the administration of the payment and will be 250 kept strictly confidential.

251

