 hear their tinnitus before the MRI scan, whether they heard the tinnitus during the scan, and whether their tinnitus
 changed since the last time asked.

All assessments will be conducted within a 4-week time-frame. Instruments are explained below.

1. The Demographics and Military Service Characteristics Form gathers information about age, sex, educational background, marital status, military status and rank, and number of deployments.

2. History of Head Injuries. The History of Head Injuries form was developed from the Defense and Veterans Brain Injury 287 Center (DVBIC) 3-Item Screening Tool (Schwab, Baker, Ivins, Sluss-Tiller, Lux & Warden, 2006; Schwab, Ivins, Cramer, 288 Johnson, Sluss-Tiller, Kiley, Lux & Warden, 2006). The DVBIC Screening Tool, initially called the Brief Traumatic Brain 289 290 Injury Screen (BTBIS), was used as the gold standard for the diagnosis of TBI in a sample of soldiers returning from duty in Iraq and/or Afghanistan (Schwab, Ivins, et al., 2006). As recommended by the DVBIC, the 3-Question Screen will be 291 292 considered positive when the participant endorses an injury (question 1) and altered consciousness (question 2, items A-293 E) for the worst head injury sustained while deployed. The form was modified for STRONG STAR and now CAP to 294 capture the number of injuries, and to answer question 2 based on the worst injury; the original form does not recognize 295 the possibility of multiple head injuries during deployment. As the 3-Question Screen does not query head injuries prior to 296 deployment, an additional four questions have been added to solicit information about each head injury sustained outside 297 of deployment.

3. MRI Screening Questionnaire will be used to exclude those with conditions that could interfere with completing the fMRI scan.

- **4. Life Events Checklist-5 (LEC-5).** The LEC-5 includes a list of 24 potentially traumatic life events commonly associated
- 301 with PTSD symptoms. The instrument was designed to facilitate the diagnosis of PTSD (Weathers, Blake, Schnurr,
- Kaloupek, Marx, & Keane, 2013a).). In this study, the LEC-5 will also be used to identify the index event and focus of the
- PTSD treatment. For each potentially traumatic life event, respondents rate their experience of that event on a 5-point nominal scale (1 = happened to me, 2 = witnessed it, 3 = learned about it, 4 = part of my job, 5= not sure, and 6 = does not

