
401 6. Generalized Anxiety Disorder-7 (GAD-7). The GAD-7 (Spitzer, Kroenke, Williams, & Lowe, 2006) will be used to assess generalized anxiety symptomology. This is a 7-item measure that asks participants to rate the frequency with 402 403 which they have been bothered by anxiety symptoms within the past two weeks on a scale ranging from 0 ("not at all") to 404 3 ("nearly every day"). Scores on all items are summed to obtain a total severity score. Scores reflect no significant 405 anxiety symptoms (0-4), mild anxiety symptoms (5-9), moderate anxiety symptoms (10-14), and severe anxiety symptoms 406 (>15). Respondents also indicate the degree to which their anxious symptoms have made it difficult for them to do their 407 work, take care of things at home, or get along with other people, from "not difficult at all" to "extremely difficult." The GAD-7 has been shown to have high internal consistency (e.g., α = .89; Lowe et al., 2008) and has been shown to reliably 408

- discriminate between anxious and non-anxious diagnostic groups (Kroenke, Spitzer, Williams, & Lowe, 2010).
- 7. Patient Health Questionnaire 9 (PHQ-9). The PHQ-9 is a widely used and well-validated instrument for measuring
 the severity of depressive symptoms (Kroenke, Spitzer, & Williams, 2001). It consists of 9 items that assess both affective

and somatic symptoms related to depression and depressive disorders; these 9 items correspond to the diagnostic criteria 412 for DSM MDD. Respondents rate the frequency with which they have been bothered by depressive symptoms within the 413 past two weeks (for baseline and follow up visits) or the past week (for interim assessment visits)on a scale ranging from 414 0 ("not at all") to 3 ("nearly every day"). Scores on all items are summed to obtain a total severity score. Scores reflect no 415 significant depressive symptoms (0-4), mild depressive symptoms (5-9), moderate depressive symptoms (10-14), 416

417 moderately severe depressive symptoms (15-19), and severe depressive symptoms (>19). Respondents also indicate the 418 degree to which their depressive symptoms have made it difficult for them to do their work, take care of things at home, or 419 get along with other people, from "not difficult at all" to "extremely difficult." The PHQ-9 has high internal consistency (e.g., alpha ranging from .83 to .92; Cameron, Crawford, Lawton, & Reid, 2008), and correlates strongly with other measures of 420 depression (Kroenke et al., 2001). 421

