- 599 Safeguards for Protecting Participants: One of the risks with assessment of mental health conditions is identification of suicidality or harm of others. Participants will be provided immediate coping tools and techniques used to manage 600 distressing emotions by a licensed therapist. Distress experienced by participants is expected to be temporary. Any 601 indication that the participant is considering suicide will be handled using processes developed by military and civilian 602 Consultants for the STRONG STAR Consortium studies. Trained clinicians and evaluators will assess history of suicide 603 and current suicidal ideation using the following standardized measures: Patient Health Questionnaire-9 (PHQ-9). For 604 605 participants identified as having low to moderate risk for suicide based on the assessment results, the patient will be allowed to remain in the study but will be referred to the research audiologist or primary care provider as applicable for 606 607 appropriate follow up within standard of care. For participants identified as being at high risk for suicide based on the assessment results, they will be excluded from the study and will be referred for more intensive treatment (outpatient or 608 609 inpatient). 610
- 611 The diagnostic assessment testing may also indicate PTSD symptoms, anxiety, depression, or alcohol use that warrants treatment, Additionally, unsuspected lesions or hearing changes may be found as a result of the research testing. In these 612 instances, a member of the Research Team will contact the participant, explain the test findings and, if appropriate, 613 encourage the participant to see their primary care provider. The research testing is not being done to diagnose health 614 615 problems, and so the participant will need to see their primary care provider to see if any action should be taken. The research team can help facilitate communication with the primary care provider and provide local resources. For active 616 duty personnel, the military command will NOT be notified, and the results of the research testing will NOT be placed in 617 618 the medical record.
- 619
- A STRONG STAR Data Safety and Monitoring Plan (DSMP) has been developed in accordance with the National
 Institutes of Health (NIH) Office of Human Research Protection (OHRP) to assure the appropriate clinical safety and
 adverse event monitoring of study subjects participating in STRONG STAR studies.
- 623

624 7.2 Potential Benefits.

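### Section 6.1.6 allows assessments up to 30 days old to be reused and does not exempt the PHQ-9, the only measure Section 7.1 names for current suicidal ideation

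*Combined protocol and SAP*

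**What the plan says.** Section 6.1.3 excludes people with "psychiatric problems and/or high suicide risk warranting immediate intervention". Under the participant safeguards in Section 7.1, trained clinicians and evaluators are to assess history of suicide and "current suicidal ideation using the following standardized measures: Patient Health Questionnaire-9 (PHQ-9". No second measure is named. The result has consequences: low to moderate risk means staying in with a referral, and high risk means exclusion and referral to more intensive care.

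Section 6.1.6 makes the Section 6.2 table the content of screening, and that table (Table 1) lists the PHQ-9 at 5 minutes. For someone arriving from another STRONG STAR study with assessments from the "past 30 days, the participant will be asked as part of the consent process to use these assessments rather than repeating" the battery, no instrument is held back. The full baseline is required in three cases: a new referral, more than 30 days elapsed, or reuse declined. In those cases the participant is told that he or "she will meet with an evaluator and complete the full baseline assessment per protocol".

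Section 6.2 gives the PHQ-9 recall period as the "past two weeks (for baseline and follow up visits"), with a past-week version for interim visits. The same section also states: "All assessments will be conducted within a 4-week time-frame".

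**The concern.** A check described as current should describe the participant at about the time of entry. For a newly referred participant it does, because screening follows consent. For a participant who accepts reuse, the text lets the only named measure be a form filled in earlier, for a different study, with a recall period that ended before consent to this one.

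What is at stake is participant safety. High suicide risk is an exclusion, and the population includes service members and veterans with PTSD. Section 7.1 itself recognises that assessing PTSD can temporarily raise symptoms. A change in risk after the earlier form would not appear on it. No estimate, test or power calculation depends on this.

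**Working it through.** The plan gives no figure to reproduce. The check sets the rules side by side and counts days.

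**Inputs**
- Reuse limit: 30 days before consent (Section 6.1.6).
- PHQ-9 baseline recall: two weeks, or 14 days (Section 6.2, PHQ-9 description).
- PHQ-9 time: 5 minutes; total assessment time: 280 to 295 minutes (Table 1).

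**Step 1: does the reuse rule reach the PHQ-9?** Screening consists of the Section 6.2 table, the PHQ-9 is in that table, and Section 6.1.6 lets earlier assessments replace repetition without naming an exception. So it does, provided the other study gave the PHQ-9. The documents do not list other studies' batteries, so this is an assumption.

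**Step 2: does any other supplied sentence require a new PHQ-9?** The sentence requiring an evaluator meeting and full baseline covers three groups, and a participant who accepts reuse is in none of them. Section 7.1 gives no timing for its check. Section 6.1.4 has a pre-screen of basic criteria, Section 6.3.2.2 asks about tinnitus around the scan, and Section 9.0 allows discontinuation for clinical worsening. None of these calls for a PHQ-9 or a suicide item.

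**Step 3: which days does a reused form describe?** A form that is k days old at consent covers days k + 14 to k before consent, and leaves the last k days uncovered.

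| Form age k at consent (days) | Days before consent covered | Days just before consent not covered |
|---|---|---|
| 7 | 21 to 7 | 7 |
| 14 | 28 to 14 | 14 |
| 30 (limit) | 44 to 30 | 30 |

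**Step 4: burden of repeating the form.** 5/295 = 1.7% and 5/280 = 1.8% of total assessment time, for reuse participants only.

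**The case against.** The strongest reply is that Section 7.1 already settles the matter. It states a specific safety duty, to assess current ideation, with no exception for reused data. Section 6.1.6 is a general convenience rule, and a 30-day-old answer is hardly current. That is a fair reading, but it shows ambiguity and does not remove it: neither section says which one governs.

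Second, the gap needs several conditions together: a participant from another STRONG STAR study, a battery no more than 30 days old, a PHQ-9 in that battery, and acceptance of reuse. If the earlier battery had no PHQ-9, there would be nothing to reuse and the form would presumably be given new. This stands, and it limits the point.

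Third, the pre-screen script, the Data and Safety Monitoring Plan and the consortium suicide procedures are cited but not supplied, and any of them could contain a fresh check. The exclusion in Section 6.1.3 is also not tied to a named instrument, and Table 1 lists the PHQ-9 as a characterisation measure. Other contacts may therefore identify risk. This stands too: the finding is that the supplied text requires no fresh PHQ-9, not that no fresh check will happen.

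Stronger readings are tempting but not supported:
- A reader might infer that the form could be 30 + 28 = 58 days old at the scan. That needs the 4-week limit to start at consent and to leave out reused forms. Section 5 could be read that way ("Study-related procedures will be completed within 4 weeks to decrease likelihood of drop-out"), but Section 6.2 speaks of all assessments, which points against it. If reused forms count, the form is at most 28 days old at the last assessment, as for anyone else, though it can still predate consent.
- A reader might infer that 30 days against 4 weeks is an error to correct. The difference is 30 - 28 = 2 days, with no demonstrated consequence. Counting reused forms within a 28-day limit would leave 28 - k days for the remaining visits, which is none for a 28-day-old form and would largely defeat reuse.
- A reader might infer that reuse participants never meet an evaluator. The text does not say so.

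**Conclusion.** The point holds in a limited form. As written, Section 6.1.6 permits the only measure Section 7.1 names for current suicidal ideation to be a form answered before consent. At the 30-day limit, that form describes about days 44 to 30 before consent. If the 4-week limit counts reused forms, the oldest usable form is 28 days old rather than 30. The gap is then smaller but remains.

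The conclusion assumes that the other study's battery included the PHQ-9 and that the unsupplied appendices and procedures do not already require a new one. The number of reuse participants is not given and cannot be estimated. The documents do not support saying that suicide risk goes unchecked in these participants. The fMRI analysis is unaffected. This is a minor, inexpensive safety improvement for the sponsor to consider.

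**What to change.** Add a sentence to Section 6.1.6 exempting the PHQ-9 from reuse. Every participant who reuses earlier assessments completes the two-week version at or after consent to this study, and a clinician or evaluator of the kind already named in Section 7.1 reviews it before the scan. The version needs naming because Section 6.2 also describes a past-week form. The 30-day allowance can stay as it is for the other instruments.

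The cost is amendment wording, about 5 minutes per reuse participant, and brief review time. No new instrument or type of staff is needed. If the consortium's procedures already include a fresh check, the amendment only puts it on record.
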